8 SUBJECT POPULATION

The study population includes approximately 256 subjects to be randomized at approximately 8 sites, with approximately 14 to 50 subjects randomized per site. To participate in the study, subjects must be 18 years old or older, current full-time wearer [REDACTED] of samfilcon A, comfilcon A, senofilcon C monthly replacement or senofilcon A 2-week replacement spherical lenses within the power range of lens powers available for the test AOHG, and currently using (during the past 1 month) a MPS (excluding OFPM) to care for their lenses. Approximately 64 subjects per habitual lens type will be randomized and recruitment of brands by sites will be competitive.

Subjects must sign the informed consent form. Subjects must be willing to discontinue artificial tears during the study and rewetting drops on the days of study visits. [REDACTED]

[REDACTED] The complete inclusion and exclusion criteria are presented in Section 1.

The enrollment for the study is planned for approximately 8 weeks. The expected duration of subject participation in the study is up to 40 days and treatment will be 30 (+3) days for all subjects [REDACTED]

An advertisement may be used to aid recruitment. If an advertisement is required, the advertisement will be submitted to the IRB for approval.

9 TREATMENTS ADMINISTERED

Upon signing the informed consent, subjects will be considered enrolled in the study and a subject identification (ID) number will be assigned by entering the subject into the electronic data capture (EDC) system by a designated staff member at the investigational site(s). The qualified subject will be randomized and assigned to either AOHG or Habitual SiHy lenses in a 1:1 ratio. Subjects in the AOHG lens group will be further randomized and assigned to either OFPM or CCP in a 1:1 ratio.

Throughout the study, the designated unmasked site personnel will be responsible for the accounting of all study products and will ensure that the study products are not used in any unauthorized manner.

9.1 Identity of Study Treatments

Test Products:

AIR OPTIX plus HYDRAGLYDE (AOHG)

OPTI-FREE PUREMOIST (OFPM)

CLEAR CARE Plus/AOSEPT Plus with
HYDRAGLYDE (CCP)

Control Products:

Johnson & Johnson ACUVUE[®] OASYS[®] Brand 2-
Week with HYDRACLEAR[®] PLUS (Oasys)

Johnson & Johnson ACUVUE[®] VITA[™] Brand Contact
Lenses (Vita)

Bausch + Lomb ULTRA[™] Contact Lenses with
MoistureSeal[™] Technology (Samfilcon A) (Ultra)

CooperVision[®] Biofinity[®] Contacts (Biofinity)

Habitual MPS (HMPS)

The study lenses will be procured by the investigational site(s). All study lenses are *Conformité Européene* (CE)-marked, FDA and Health Canada approved, and will be sourced from commercial stock, including commercial packaging and labelling. Assigned lenses will be masked to the Investigator and subject. This will be accomplished by an unmasked

[figure not shown]
[figure not shown]
[figure not shown]
coordinator dispensing the commercially packaged study lenses assigned to the subject with the blister label removed.

OFPM will be supplied in sterile 10 fl. Oz. (300 mL) filled bottles with investigational labelling. A new lens case will be supplied with each bottle.

CCP will be supplied in sterile 12 fl. Oz. (355 mL) filled bottles with investigational labelling. A new lens case will be supplied with each bottle.

Table 9-1 Study Treatment OFPM and CCP

Properties	OFPM (Test product)	CCP (Test product)	HMPS (Control product)
Administration	Subjects will use OFPM to store and disinfect their contact lenses as instructed by the study site personnel, dispensing the solution according to the instructions for use.	Subjects will use CCP to store and disinfect their contact lenses as instructed by the study site personnel, dispensing the solution according to the instructions for use.	Subjects will use their HMPS to store and disinfect their contact lenses as instructed by the study site personnel, dispensing the solution according to the instructions for use.
Duration of Treatment	The subject will wear their assigned lenses in a daily wear modality for 30 (+3) days using OFPM daily to care for their lenses.	The subject will wear their assigned lenses in a daily wear modality for 30 (+3) days using CCP daily to care for their lenses.	The subject will wear their assigned lenses in a daily wear modality for 30 (+3) days using their HMPS daily to care for their lenses.
Quantity/Dose	Up to 32 cleaning and disinfecting cycles will be used for the study.	Up to 32 cleaning and disinfecting cycles will be used for the study.	Up to 32 cleaning and disinfecting cycles will be used for the study.
Supply	OFPM will be supplied sterile, in 10 fl. Oz. (300 mL) filled bottles with	CCP will be supplied sterile, in 12 fl. Oz. (355 mL) filled bottles with investigational	HMPS will either be: 1) Purchased by the subject and reimbursed. The

	
investigational labelling. A new lens case will be supplied with each bottle.
 
The product is manufactured by Alcon Laboratories in Fort Worth, Texas.
 
The study kit will contain one bottle of the test solution (bottle will be re-labeled), and green and white screw top case.
 	
labelling. A new lens case will be supplied with each bottle.
 
The product is manufactured by Alcon Laboratories in Fort Worth, Texas.
 
The study kit will contain one bottle of the test solution (bottle will be re-labeled), and the lens cup that contains platinum disk for neutralization of the solution.
 
Marketed sterile saline (B&L SENSITIVE EYES PLUS SALINE in commercial packaging) will be provided separate from the kit by the unmasked study coordinator to each subject to use for rinsing lenses and cases as needed.
 	
unmasked site personnel must confirm at Visit 2 that the solution purchased by the subject was the HMPS identified during screening and that is not expired.
 
2) Purchased by the site according to the HMPS identified during screening and dispensed to the subject for use during the study.
 
HMPS will be dispensed/used in commercial packaging. The manufacturer information for each product can be found in the package insert.
 
--	---	--	--

--	--	--	--

OFPM and CCP will be provided in the commercial bottle but will be re-labeled in local language. Included on the investigational labels for the randomized product will be the kit number, protocol number, fill volume, storage conditions, the indicator “Disinfecting Solution” and a statement that the product is for investigational use only. OFPM and CCP should be stored at room temperature or below.

Additionally, the following warning will be included on the investigational label for CCP: “IMPORTANT: Misuse will result in burning and stinging. Use only lens case provided. Do not remove lenses from the lens case for at least 6 hours. The solution needs time to neutralize. Never rinse lens with product prior to insertion. Red snap cap means product is not for direct use on eye.”

More information on the OFPM, CCP, or HMPS can be found in the Product Labeling. Refer to the MOP for product labels for OFPM and CCP.

The new label will be sufficient to mask the OFPM and CCP, thus maintaining the subject masking to brand. A designated unmasked staff member (other than the Investigator) at the site will be assigned to dispense the sealed test kit and the HMPS to ensure Investigator masking. Unmasked site personnel cannot conduct study specific procedures.

9.2 Usage

The subjects will use the study lenses bilaterally according to the Instructions for Use provided by the product manufacturer, as instructed by the designated site personnel. All study lenses will be dispensed by a trained, unmasked staff member and provided to the subjects.

The subjects will wear the assigned lenses (AOHG or Habitual SiHy) [REDACTED]. [REDACTED]. Subjects assigned to the senofilcon A 2-week replacement lenses will be asked to return to the site to be dispensed in a masked manner [REDACTED]. [REDACTED]. All unplanned lens replacements must be documented in EDC.

[figure not shown]
Subjects assigned to the AOHG lenses will be instructed to care for the lenses daily using either OFPM or CCP, according to randomized assignment of product. Subjects assigned CCP will be provided with B&L SENSITIVE EYES PLUS SALINE as a rinsing solution. AOHG lens care solutions will be provided by the Sponsor. Subjects assigned to the Habitual

SiHy lenses will be instructed to care for the lenses daily using their HMPS according to the products' instructions for use. A new bottle of the HMPS to be used for the study will either be purchased by the subjects and confirmed by the masked investigational site personnel or purchased by the site.

[figure not shown]
[Redacted]

[Redacted]

[Redacted]

[figure not shown]
[figure not shown]
[figure not shown]
[figure not shown]
10 STUDY PROCEDURES

10.2 Visits and Examinations

10.2.1 Visit 1 – Screening

[figure not shown]
[figure not shown]
[figure not shown]
[figure not shown]
	Note: Potential subjects should be instructed to attend Visit 1 (Screening) wearing their habitual contact lenses and to bring their HMPS (used or unused bottle).
1	Have the subject or legally authorized representative read, sign, and date the IEC-approved informed consent document. Additionally, have the individual obtaining consent from the subject and a witness, if applicable, sign and date the informed consent document. Provide a photocopy of the signed document to the subject and place the original signed document in the subject's chart.
2	Enter the subject into EDC in order to obtain their 5-digit subject ID number. Note: Obtain subject ID number for all subjects who signed an informed consent form (including screen failures).

3	Obtain demographic information, contact lens and lens care history, and medical history, including information on all medications used within the past 30 days. Include herbal therapies, vitamins, and all over-the-counter as well as prescription medications.
4	
5	
6	
7	
8	
9	Perform biomicroscopy assessment using slit-lamp examination scales. For details and order of staining procedures, refer to MOP.
10	Assess and record any AEs that are observed or reported from the time of informed consent (see Section 12).

11	Review inclusion/exclusion criteria to determine if the subject qualifies to be randomized in the study. The unmasked site personnel must confirm randomization by entering applicable details of eligibility in the EDC system and obtain assignment of study lens/lens care treatment group.
12	Schedule Visit 2 (Day 1 Insertion) within 1-7 days of Visit 1 (Screening).
13	
Remind subjects that spectacles or habitual contact lenses/lens care solutions can continue to be used until the day prior to Visit 2. Habitually worn lenses can be returned or a new pair dispensed. [REDACTED]
 
[REDACTED]
 
[REDACTED]
 
Subjects randomized to habitual SiHy/MPS must have a new bottle of the HMPS, identified during screening, ready for dispensing at Visit 3. This can be accomplished in two ways for the study:
 
 1) The subject purchases a new bottle of the HMPS and brings it to Visit 2. In this case the subject will be reimbursed for their purchase. The unmasked coordinator must confirm the solution purchased was the HMPS identified during screening and that it is not expired. The unmasked coordinator will dispense the purchased HMPS at Visit 3. 2) The site purchases the subject’s HMPS and the unmasked coordinator dispenses to the subject at Visit 3.

10.2.2 Visit 2 (1-7 Days from Visit 1) – Day 1 Insertion Visit

[figure not shown]
1	Obtain information on any changes in medical health and/or the use of concomitant medications since previous visit.
2	Perform biomicroscopy assessment using slit-lamp examination scales with no conjunctival/corneal staining procedures. Refer to MOP for details.
3	[REDACTED]

4	Unmasked coordinator to dispense randomized study lenses. Record time of lens insertion.
5	
6	
7	
8	
9	
10	Assess and record any AEs that are observed or reported (see Section 12).

11	Record any Device Deficiencies that are observed or reported (see Section 12).
12	

10.2.3 Visit 3 - Day 1: after approximately 8 hrs (± 30 mins)

	Note: Subjects must respond to the 8 hrs text message questionnaire prior to proceeding with Visit 3.
1	Obtain information on any changes in medical health and/or the use of concomitant medications since previous visit.
2	
3	Perform biomicroscopy assessment with lenses on the eye using slit-lamp examination scales with no conjunctival/corneal staining procedures. Refer to MOP for details.
4	

[figure not shown]
5	
6	
Unmasked coordinator to assign and dispense study lens care solutions
 
- Ensure test solutions are provided per randomized group assignment - masked label to subjects.- HMPS to be purchased by subject or provided by site. Subject/site will be reimbursed. Site to confirm correct unexpired HMPS dispensed if subject is purchasing the HMPS.- Review product instructions for use with subjects. 
Educate subjects assigned to CCP product and B&L SENSITIVE EYES PLUS SALINE on the use of correct lens case with the product.

7	
Assess and record any AEs that are observed or reported (see Section 12).

8	
Record any Device Deficiencies that are observed or reported (see Section 12).

9	
Unmasked coordinator to instruct subjects assigned the 2-week replacement lenses to return to site on Day 15 (± 1 Day).
 
Schedule lens replacement in office.
 
Collect initial 2-week lenses. Refer to MOP for details.
 
Unmasked coordinator to dispense replacement 2-week lenses.
 

10	[Redacted]
----	------------

10.2.4 Visit 4 - Day 30 (+3 days): 8 hrs (±30 min)/Exit

	Note: Ensure subjects answered the 6 hrs text message questionnaire based on lenses worn during Day 30 prior to proceeding with Visit 4.
1	[Redacted]
2	Obtain information on any changes in medical health and/or the use of concomitant medications since Visit 3.
3	[Redacted]
4	[Redacted]
5	[Redacted]

6	[REDACTED]
7	[REDACTED]
8	Assess and record any AEs that are observed or reported (see Section 12).
9	Record any device deficiencies that are observed or reported (see Section 12).
10	Collect worn study lenses for shipment and analysis. Record time of lens removal. Refer to MOP for details.
11	Exit the subject from the study.

10.4 Discontinued Subjects

Discontinued subjects are those who withdraw or are withdrawn from the study after being randomized. Subjects may discontinue from the study at any time for any reason. Subjects may also be discontinued from the study at any time if, in the opinion of the Investigator, their continued participation poses a risk to their health. Discontinued subjects will not be replaced (ie, their subject numbers will not be re assigned/re-used).

If a subject is identified not to fulfill the eligibility criteria for study inclusion during the Screening visit [REDACTED], the subject will be screen failed and will not participate any further in the study. The EDC system will be updated to confirm the subject is a screen failure. The Investigator will explain to the subject the reason(s) why eligibility was not met and provide appropriate information/treatment, if required. The Exit form will be completed for all discontinued subjects and screen failures.

Should a subject exhibit any clinically relevant signs, symptoms, or other clinical observations that possibly could be associated with suspected sensitivity or intolerance to one of the study treatments, the Investigator must document those observations on an AE Form. Observations must also be reported for occurrences not associated with any study treatment (see Section 12.3, Procedures for Recording and Reporting AEs and SAEs).

Any subject who exits early from the study should undergo all procedures outlined at [REDACTED]/Exit. Additionally, the Exit Form must be completed and the reason for discontinuation must be identified and captured in EDC.

Finally, to ensure the safety of all subjects who discontinue early, Investigators should assess each subject and, if necessary, advise them of any therapies and/or medical procedures that might be needed to maintain their health.

10.5 Clinical Study Termination

If the clinical study is prematurely terminated or suspended, the Sponsor will inform the Investigator and the regulatory authorities of the termination/ suspension and the reason(s) for the termination/suspension. The Investigator should promptly notify the IEC/IRB of the termination or suspension and of the reasons. The Sponsor reserves the right to close the investigational site or terminate the study in its entirety at any time, for reasonable cause. Reasons for the closure of an investigational site or termination of a study may include:

- Successful completion of the study
- The study's enrollment goals are met
- The Investigator fails to comply with the protocol or GCP guidelines
- Safety concerns
- Sufficient data suggesting lack of efficacy
- Inadequate recruitment of subjects by the Investigator

The Investigator also may terminate the study at his/her site for reasonable cause. If the Sponsor terminates the study for safety reasons, it will immediately notify the Investigator(s) by telephone and subsequently will provide written confirmation of and instructions for study termination.

11 ANALYSIS PLAN

11.1 Subject Evaluability

The final subject evaluability will be determined prior to breaking the code for masked treatment assignment and locking the database.

[figure not shown]
11.2 Analysis Data Sets

11.2.1 Safety Data Set

Safety analyses will be conducted using the safety analysis set on a treatment-emergent basis. The safety analysis set will include all subjects/eyes exposed to the study lens and/or the study lens care system (LCS) evaluated in this study as a regimen. For treatment-emergent safety analyses, subjects/eyes will be categorized under the actual lens or regimen exposed.

11.2.2 Full Analysis Data Set

The FAS is the set of all randomized subjects who are exposed to a study lens on Day 1 or a study regimen (lens and LCS) thereafter.

11.3 Demographic and Baseline Characteristics

Demographic information (age, sex, ethnicity, race) will be summarized on the safety, full,

11.4 Efficacy Analyses

[figure not shown]
This study defines one primary endpoint [redacted]. All efficacy evaluations will use the FAS as the primary analysis set. [redacted]

[figure not shown]

11.4.1 Primary Efficacy

The primary objective of this study is to demonstrate less cholesterol uptake with each of the test regimens (AOHG/OFPM, AOHG/CCP) compared to each of the control regimens (Biofinity/HMPS, Vita/HMPS, Ultra/HMPS, Oasys/HMPS).

The corresponding endpoint is the cholesterol uptake (deposits) measured from worn lenses at Day 30 (2-week wear of Oasys and 30-day wear for other), for each of the test and control regimens. OD lenses from approximately 25 subjects per regimen will be analyzed for the *ex vivo* analysis.

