Material: Lotrafilcon B, 33% water content with plasma surface treatment

Base curve: 8.6 millimeters (mm)

Diameter: 14.2 mm

Power range:

+8.00 Diopters (D) to -12.00 D (0.50 D steps above +6.00 D and -10.00) Lenses will be worn daily wear and cared for (up to 32 cleaning and disinfecting cycles) with CCP or OFPM as randomized.

Bausch + Lomb (B&L) Sensitive Eyes[®] Plus Saline will be provided as a rinsing solution to those randomized to CCP.

Test lens care solutions will be over labeled to mask the brand. See the Manual of Procedures (MOP) for detailed instructions for use of test lens care products.

Sponsor:

Alcon Research, Ltd.
[name]

Protocol Number:

Control Products:

Habitual Spherical SiHy Lenses:

Bausch + Lomb ULTRA™ Contact Lenses with MoistureSeal™ Technology (Samfilcon A) (Ultra)
Material: samfilcon A, 46% water content
Base curve: 8.5 mm
Diameter: 14.2 mm
Power range: +6.00 D to -12.00 D (0.50 D steps above -6.00 D)

Johnson & Johnson ACUVUE® VITA™ Brand Contact Lenses (Vita)Material: senofilcon C, 41% water content
Base curve: 8.4, 8.8 mm
Diameter: 14.0 mm
Power range: +8.00 D to -12.00 D (0.50 D steps above +/-6.00 D)

Johnson & Johnson ACUVUE® OASYS® Brand 2-Week with HYDRACLEAR® PLUS (Oasys)
Material: senofilcon A, 38% water content
Base curve: 8.4, 8.8 mm
Diameter: 14.0 mm
Power range: +8.00 D to -12.00 D (0.50 D steps above +/-6.00 D)

Biofinity

Material: comfilcon A, 48% water content
Base curve: 8.6 mm
Diameter: 14.0 mm
Power range: +8.00 D to -12.00 D (0.50 D steps after +/-6.00 D)

Route of Administration: Lenses will be dispensed by the

Sponsor:

Alcon Research, Ltd.
[name]

Protocol Number:

unmasked study staff member(s) so that the subject does not see the lens label and will remain masked to the details of the lens.

Subjects will use the lenses as instructed by the coordinator, according to the instructions for use.

Duration of Treatment:

Subjects will wear the lenses bilaterally for a total duration of 30 days (-0, +3 days). Oasys lenses will be replaced (masked dispensing) at Day 15 ±1 day.

The lenses will be removed every night during the study.

Parameters:

The lenses will be available in the powers offered by each brand that are inclusive of the powers offered by AOHG (+8.00 D to -12.00 D).

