The lenses will be worn as daily wear and cared for with subject's HMPS (up to 32 cleaning and disinfection cycles). The HMPS will be purchased by the subject (confirmed by the site) or purchased by the site and used in the commercial packaging according to the product's instructions for use.

Subject Selection:

Inclusion Criteria:

1. Subjects must be at least 18 years of age and sign the informed consent document
2. Subjects' vision must be correctable to 0.1 (logMAR) or better in each eye at distance with habitual lenses at Visit 1.
3. Manifest cylinder (at screening) less than or equal to 0.75 D in each eye and spectacle add < +0.50 D in each eye.
4. Current full-time wearer (during the past 1 month for a minimum of 5 days per week and 6 hours per day) of spherical samfilcon A, comfilcon A, or senofilcon C

Sponsor:

Alcon Research, Ltd.
[name]

Protocol Number:

- monthly replacement lenses or senofilcon A 2-week replacement lenses within the power range of lens powers available for the test AOHG spherical lenses.
5. Current user (for the past 1 month) of an MPS (excluding OFPM) to care for their lenses.
 6. Willing to answer text messages on a daily basis during the study.
 7. Willing to discontinue artificial tears during the study and rewetting drops on the days of study visits.
 8. Uses digital devices (eg, smart phone, tablet, laptop computer, or desktop computer) for 20 consecutive minutes at least twice a week and willing to continue the same pattern for the duration of the study.

Exclusion Criteria:

1. Habitual lens wear in an extended wear modality (routinely sleeping in lenses overnight for 1 or more nights per week).
2. Unstable tear film with a NIKBUT < 6 seconds in either eye without lenses.
3. Any anterior segment infection, inflammation, disease or abnormality that contraindicates contact lens wear as determined by the Investigator (within 7 days of enrollment, or current).
4. History of herpetic keratitis, corneal surgery or irregular cornea.
5. Prior refractive surgery (eg, laser assisted in situ keratomileusis and photorefractive keratectomy).
6. Any use of systemic or ocular medications for which contact lens wear could be contraindicated as determined by the Investigator.
7. Subjects who are currently using or have not discontinued Restasis[®], Xiidra[™] and/or topical steroids within the past 7 days.

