5.2 Known and Potential Risks

Safety information on AOHG, OFPM, and CCP may be found in the products' labeling. The Investigator should advise subjects of the following general warnings and precautions with contact lens wear, including the following:

- Serious eye injury, scarring of the cornea and loss of vision may result from problems associated with wearing contact lenses and using lens care products.
- Eye problems, including infection, corneal ulcers, corneal neovascularization, or iritis can develop rapidly and lead to loss of vision if left unattended.
- Smoking and/or swimming increases the risk of corneal ulcers with contact lens wear, especially when lenses are worn overnight or while sleeping.
- The risk of ulcerative keratitis has been shown to be greater among users who wear their lenses overnight compared to those who do not wear them overnight.

The risks with contact lens wear are increased with a pre-existing or active ocular infection or inflammation, improper lens fit, and/or noncompliance with regimen. The AOHG contact lenses are for daily use and are to be cared for with CCP or OFPM at the end of each day. Subjects who fail to follow the instructions for replacing and caring for their contact lenses could experience an eye infection of the cornea or injury. A corneal ulcer could develop rapidly and lead to loss of vision. An improperly fitted contact lens may affect corneal curvature and result in vision fluctuations upon lens removal.

Potential serious complications with contact lens wear are usually accompanied by 1 or more of the following signs or symptoms:

- Moderate to severe eye pain not relieved by removing the lens
- Foreign body sensation
- Excessive tearing/ocular secretions including mucopurulent discharge
- Ocular hyperemia

- Photophobia
- Burning, stinging, itching, or other pain associated with the eyes
- Comfort is less compared to when the lens was first placed on the eye
- Poor VA/blurred vision
- Rainbows or halos around objects
- Feeling of dryness

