Subjects should be instructed to remove the lenses if any of the above signs or symptoms are noticed. A serious condition such as a corneal ulcer, infection, or iritis may be present, and may progress rapidly. Less serious reactions such as abrasions, infiltrates, and bacterial conjunctivitis must be managed to avoid more serious complications. In addition, the Investigator should advise subjects of possible ocular dryness, increased lens awareness/intolerance, and visual changes with concomitant medications or during pregnancy.

It is important for OFPM and CCP users to follow directions and all labeling instructions for proper use, including use of the lens case. Subjects who are noncompliant and fail to follow the instructions for cleaning, storage, and disinfection of their contact lenses could experience an eye infection or injury. Contact lens wearers unfamiliar with a hydrogen peroxide solution (CCP) could inadvertently use the peroxide solution as a lubricating/rewetting drop or rinse their contact lenses prior to insertion, resulting in chemical burn due to the unneutralized peroxide solution. Additionally, using the wrong lens cup, overfilling the lens cup with peroxide solution or disinfecting the lenses for less than the specified time can result in incomplete neutralization of the peroxide solution. In such cases, adverse ocular effects such as discomfort, burning, stinging, pain, inflammation or irritation as well as chemical burn or irritation to the fingers may occur. These adverse effects are usually temporary, and users should be instructed to immediately flush the eyes or fingers with saline or water should this occur. Overall, the potential risks associated with use of the subject's Habitual SiHy/MPS, AOHG/OFP, and AOHG/CCP are similar when used as indicated.

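### Does replacing the Oasys lenses at Day 15 and collecting at Day 30 break the 2-week wear named in the primary endpoint?

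*Protocol*

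**What the plan says.** Section 11.4.1 of the protocol defines the primary endpoint as uptake "measured from worn lenses at Day 30 (2-week wear of Oasys and 30-day wear for other" lenses. The synopsis (Assessments) places the assay on right-eye lenses collected at Day 30.

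The schedule is in the synopsis, under Control Products: "Subjects will wear the lenses bilaterally for a total duration of 30 days (-0, +3 days"), and "Oasys lenses will be replaced (masked dispensing) at Day 15 ±1 day". Section 2 repeats the Day 15 ±1 dispensing in a footnote. Section 10.2.3 has the unmasked coordinator tell "subjects assigned the 2-week replacement lenses to return to site on Day 15", with one day's tolerance either way. Study lenses are first inserted on Day 1 (section 10.2.2) and collected at Day 30 (+3) (section 10.2.4).

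The fourth inclusion criterion describes the eligible habitual lenses as "monthly replacement lenses or senofilcon A 2-week replacement lenses". On use, section 9.2 states: "The subjects will use the study lenses bilaterally according to the Instructions for Use provided by the product manufacturer". On risk, section 5.2 warns: "Subjects who fail to follow the instructions for replacing and caring for their contact lenses could experience an eye infection". It also says that the risks of the habitual regimen, "AOHG/OFP, and AOHG/CCP are similar when used as indicated".

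**The concern.** Two pairs of 2-week lenses cover 28 days, but the shortest permitted time from first insertion to exit is longer than that. So even a fully compliant subject at a fully compliant site wears at least one Oasys pair beyond 14 days.

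Two things could be at stake. First, the assayed Oasys lens may be older than section 11.4.1 says. If cholesterol uptake is still rising after two weeks, the extra wear raises the Oasys values and tilts those comparisons towards the test regimens. Second, if 2 weeks is taken as a binding replacement limit, the schedule seems to conflict with the statement in section 9.2 that lenses are used as the manufacturer instructs, and with risk statements in section 5.2 that presuppose such use.

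**Working it through.** **Inputs.** First insertion is on Day 1 (section 10.2.2). The replacement day is r = 14, 15 or 16 (synopsis; sections 2 and 10.2.3). The exit day is e = 30, 31, 32 or 33 (synopsis; sections 2 and 10.2.4). The stated Oasys wear is 2 weeks = 14 days (section 11.4.1).

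**Formulas, in elapsed days.** First pair = r − 1. Second pair = e − r. Sum = e − 1.

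| Replacement day | First pair | Second pair, exit Day 30 | Day 31 | Day 32 | Day 33 |
|---|---|---|---|---|---|
| 14 | 13 | 16 | 17 | 18 | 19 |
| 15 | 14 | 15 | 16 | 17 | 18 |
| 16 | 15 | 14 | 15 | 16 | 17 |

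- **Both pairs.** The sum is 29 to 32 days against 2 × 14 = 28, an excess of 1 to 4 days. None of the 12 combinations keeps both pairs at or below 14 days.
- **The assayed pair.** Lenses collected at Day 30 are the second pair. On schedule it is worn 30 − 15 = 15 days, one more than the label. The range is 14 to 19 days. It exceeds 14 in 11 of 12 combinations; the exception is Day 16 with Day 30. These are counts of combinations, not probabilities.
- **Other ways of counting.** In calendar wear days with the swap at the start of the replacement day, the second pair is worn e − r + 1 days: 16 on schedule and 15 to 20 within the windows. The conclusion about both pairs together is the same.

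**The same count for the other lenses.** Section 11.4.1 calls their wear 30 days. In elapsed days it is e − 1 = 29 on schedule and 29 to 32 within the window. On schedule, each label in that sentence is one elapsed day away from the actual figure: Oasys 15 against 14, the others 29 against 30. Both figures are therefore rounded names for visit intervals.

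**Wear time of test against Oasys.** For the same exit day the ratio is (e − 1)/(e − r). On schedule it is 29/15 = 1.93. The lowest is 32/19 = 1.68 (r = 14, e = 33) and the highest is 29/14 = 2.07 (r = 16, e = 30).

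**Extent.** Habitual Oasys wearers number about 64, randomized 1:1, so 64 × 1/2 = 32 are Oasys controls; about 25 per regimen are assayed (section 11.4.1). The comparisons affected are 2 test regimens × 1 of 4 controls = 2 of 8.

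**Use and risk statements.** None of the three sentences gives a number of days. The sentence in section 9.2 and the warning in section 5.2 point to instructions that the protocol does not reproduce. The warning concerns subjects who do not comply, not a replacement visit that the protocol itself schedules. The synopsis objective also mentions a recommended replacement period, but the phrase stands with the AOHG lenses and their solutions and most naturally describes AOHG wear.

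**The case for a change.** The strongest case for a change is that the mismatch is internal and does not depend on adherence. The exit window opens only to the late side, so it can only lengthen wear. At its extreme the assayed lens is 19 days old, 5/14 = 36% beyond two weeks, and that is hard to call 2-week wear. The protocol repeatedly calls Oasys a 2-week lens while appealing to correct replacement in its use and risk sections. Stating the actual wear range would cost little.

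The arithmetic stands, and so does the point that the label is loose at the edge of the windows. The rest does not carry through:

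- The finding that no combination works depends on the first pair, which is not the endpoint lens. For the endpoint lens the on-schedule difference is one day.
- The tolerances are stated openly wherever the schedule is given. Sites are told Day 15 ±1 and can follow it; no legible text gives them a 14-day maximum to breach.
- A conflict with sections 5.2 and 9.2 needs the content of the Instructions for Use. Putting the 2-week product description in their place assumes what has to be shown. Section 9.2 is also redacted where it describes wear and re-dispensing, although redacted text could not make two pairs cover 29 days within 14 days each.

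**Conclusion.** No change to the plan follows. The phrase in section 11.4.1 is approximate: the assayed Oasys lens is worn 15 elapsed days on schedule and 14 to 19 within the windows. The description and the schedule do not match to the day, and reconciling them is a matter of wording.

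The effect on uptake cannot be sized, because the legible protocol gives neither an Oasys mean nor data on uptake over time. If uptake has levelled off by two weeks, the effect is nil. If it is still rising, the extra Oasys wear favours the test regimens slightly, but the same assumption makes the longer AOHG wear (1.68 to 2.07 times the Oasys wear) work against them. Six of the eight comparisons, those with Biofinity, Vita and Ultra, are untouched.

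Analysts can also fill the gap. Insertion time on Day 1 and removal time at exit are recorded, and the planned Oasys replacement takes place in the office, so the age of the assayed lens can be described when results are reported. Such a summary commonly belongs in the SAP, which is not at hand.

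This conclusion assumes daily wear throughout and no planned replacement other than the one visible. It takes no position on what the correct replacement interval is.
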